### **5.2 Derived datasets**

At the moment of the preparation of the present SAP, three derived dataset is forecasted to be created, i.e. the one containing the MedDRA codes for the Adverse Events, the one containing the information about the adherence to the device and the one containing the analysis populations, that will be prepared after the database freezing. In case additional derived dataset will be needed during the analysis phase, details will be provided in the Statistical Report.

## **6 PATIENTS CHARACTERISTICS AT BASELINE**

### **6.1 Patients' Disposition**

The patients' enrolment will be summarized (Appendix 2: Table D.1) and listed (Appendix 3: Listing D.1). Enrolled, completed and not completed patients, including the reasons, will be summarized with frequency and percentages.

### **6.2 Inclusion and Exclusion criteria**

	e-CIG VS. IQOS Statistical Analysis Plan Version 2.0	Doc code: BIOSTAT.SAP.02
		Pag. 11 of 115

The data of the Inclusion and exclusion criteria for all the screened patients will be listed (Appendix 3: Listings D.2 and D.3).

### **6.3 Demographics and smoking habits**

The following demographic and baseline variables will be analyzed: age, gender at birth and education (Appendix 2: Table D.2a). As for the smoking habits, a dedicated table, in which details are presented as summary and frequency tables, will be prepared. Number of cigarettes per day will be summarized (Appendix 2: Table D.2b).

These data will also be listed (Appendix 3: Listing D.4, Listing D.5).

### **6.4 Medical History**

The medical conditions will be coded with the MedDRA dictionary (last available version) and be analyzed as previous and present Medical History using the variable "Ongoing" for creating the two sets of data. The past and present incidence of the different conditions by system organ class and preferred term will be described with frequencies and percentages (Appendix 2: Tables D.3 and D.4a). Present Medical History is defined "In treatment" if the disease is still being treated at the time of the signing of the informed consent and "Not in treatment" otherwise. Present Medical History In treatment and Not in treatment will be summarized through further tables. (Appendix 2: Tables D.4b and D.4c)

These data will also be listed (Appendix 3: Listings D.6, D.7, D.8, D.9).

### **6.5 Patients' Characteristics and Vital Signs at Baseline**

The values of each vital sign variable, i.e. Height, Weight, BMI, FatM, FatP, Total Body Water, Fat Free Mass, Body Muscle Mass, Body Bone Mass, Metabolica Age, Visceral Fat, PAS, PAD and HR will be summarized at baseline in each group through n, missing, mean, standard deviation, (25th, 50th, 75th) percentiles (Appendix 2: Table D.5). These data will also be listed (Appendix 3: Listing S.2).

### **6.6 Urine collection and storage**

Urine collection and storage will be summarized in each group with frequency table regarding to the device given to the subject and with descriptive statistics for the containers delivered (Appendix 2: Table D.6). These data will also be listed (Appendix 3: Listing D.10).

### **6.7 Fagestorm test for nicotine dependence**

	e-CIG VS. IQOS Statistical Analysis Plan Version 2.0	Doc code: BIOSTAT.SAP.02
		Pag. 12 of 115

The results of the Fagestorm test for nicotine dependence (FTCD) will be presented as frequencies and percentages for the single questions and total scores derived from the questionnaire through n, missing, mean, standard deviation and 25th, 50th, 75th percentiles (Appendix 2: Table D.7). These data will also be listed (Appendix 3: Listing D.11).

## 6.8 Step test

The values of Step Test, i.e Baseline, Step 1 to 5 and will be summarized by HR and SpO2 in each group through n, missing, mean, standard deviation and 25th, 50th, 75th percentiles (Appendix 2: Table D.8a). The other items at baseline, i.e. Baseline condition recovery time, Stop time and V02MAX (see Section 7.5 for the definition) will be summarized similarly (Appendix 2: Table D.8b). These data will also be listed (Appendix 3: Listing D.12)

## 6.9 Device delivery

The data of the device delivery regarding the preferred flavor of chopstick chosen, the device's functioning and the patient training for the device will be summarized in each group through frequency tables for all screened subjects (Appendix 2: Table D.9) and will be listed (Appendix 3: Listings D.13).

# 7 STATISTICAL ANALYSES OF THE EFFICACY ENDPOINTS

The analyses of the primary and secondary endpoints will be carried out of both the ITT and PP populations. Moreover, as for the Step Test and the Quality of Life (i.e. EQ-5D), a further analysis in the subpopulation of the "Continuous Quitter" will be presented.

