## 7.1 Analysis of primary endpoint

The primary endpoint aims to compare the efficacy of HnB and EC in terms of quit rates at week 12 by means a non-inferiority threshold of 15%.

A "Continuous Quitter" is defined as a subject who has a number of conventional cigarette/day equal to zero from Visit 4 to Visit 6. The Farrington-Manning Score Test for Proportion Difference will be used for comparing the quit rates of the two groups. The SAS® PROC FREQ with the METHOD=FM option will be used. The quit rates of the two groups, along with the relevant 95% Confidence Intervals, will be summarized in Table E.1 (Appendix 2).

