## **7.4 EQ-5D**

The Euro Quality of Life Questionnaire (EQ-5D) will be presented as descriptive summary table by visit. Acceptability of HnB and of EC will be analyzed through the assessment of several questionnaires. The analyses will be presented through the five dimensions (i.e. Mobility, Self-Care, Usual Activities, Pain/Discomfort, Anxiety/Depression) and a Visual Analogue Scale (EQ VAS). Changes from the Baseline Visit to all the subsequent study visits will be also generated. The results will be included in Table E.6 (Appendix 2).

The t-test will be carried out on the differences at final visit to baseline. In case the normality assumption is not verified, the corresponding non parametric test will be adopted. The results will be

	e-CIG VS. IQOS Statistical Analysis Plan Version 2.0	Doc code: BIOSTAT.SAP.02
		Pag. 16 of 115

included in Table E.4a2 (Appendix 2). These data will also be listed (Appendix 3: Listing E.1). The analysis will be presented by all subjects and “Continuous Quitters”.

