### 7.5 Step test by visit

The Step test data will be presented as descriptive summary table by visit. The seven items regarding Heart Rate and Oxygen Saturation (i.e. Baseline, Step 1 to 5 and Baseline condition recovery time) will be analysed by HR and SpO2. The two items, (i.e. Stop time and VO2MAX, will be analysed using the same methods (Table E.7a). In details, the latter, is the result of the so called “Chester Step Test” who was computed for each subject at site and reported in the eCRF.

An inferential analysis will be carried out on the changes from baseline by item. The results will be presented in Table E.7b. The data will also be listed (Appendix 3: Listing D.8). The analysis will be presented by all subjects and “Continuous Quitters”.

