Table E.5 Summary of the Biomarkers of Biological Exposure (BoBE) - eCO (ppm)  
Population: <Per-Protocol/Intention-To-Treat>

	Visit	Observed Values at Visit						Changes From Visit 1 to Visits n							
		N	N miss	Mean	STD	CI 95%	Median	Range (Q1-Q3)	N	N miss	Mean	STD	CI 95%	Median	Range (Q1-Q3)
Group HnB	Screening	XX	XX	XX.XX	XX.XX	[XX.XX,XXX.X]	XX.XX	(XX.XX - XXX.X)							
	Visit 1	XX	XX	XX.XX	XX.XX	[XX.XX,XXX.X]	XX.XX	(XX.XX - XXX.X)							
	Visit 2	XX	XX	XX.XX	XX.XX	[XX.XX,XXX.X]	XX.XX	(XX.XX - XXX.X)							
	Visit 3	XX	XX	XX.XX	XX.XX	[XX.XX,XXX.X]	XX.XX	(XX.XX - XXX.X)							
	Visit 4	XX	XX	XX.XX	XX.XX	[XX.XX,XXX.X]	XX.XX	(XX.XX - XXX.X)							
	Visit 5	XX	XX	XX.XX	XX.XX	[XX.XX,XXX.X]	XX.XX	(XX.XX - XXX.X)							
	Visit 6	XX	XX	XX.XX	XX.XX	[XX.XX,XXX.X]	XX.XX	(XX.XX - XXX.X)							
	Follow-up	XX	XX	XX.XX	XX.XX	[XX.XX,XXX.X]	XX.XX	(XX.XX - XXX.X)	XX	XX	XX.XX	XX.XX	[XX.XX,XXX.X]	XX.XX	(XX.XX - XXX.X)
Group EC	Screening	XX	XX	XX.XX	XX.XX	[XX.XX,XXX.X]	XX.XX	(XX.XX - XXX.X)							
	Visit 1	XX	XX	XX.XX	XX.XX	[XX.XX,XXX.X]	XX.XX	(XX.XX - XXX.X)							
	Visit 2	XX	XX	XX.XX	XX.XX	[XX.XX,XXX.X]	XX.XX	(XX.XX - XXX.X)							
	Visit 3	XX	XX	XX.XX	XX.XX	[XX.XX,XXX.X]	XX.XX	(XX.XX - XXX.X)							
	Visit 4	XX	XX	XX.XX	XX.XX	[XX.XX,XXX.X]	XX.XX	(XX.XX - XXX.X)							
	Visit 5	XX	XX	XX.XX	XX.XX	[XX.XX,XXX.X]	XX.XX	(XX.XX - XXX.X)							
	Visit 6	XX	XX	XX.XX	XX.XX	[XX.XX,XXX.X]	XX.XX	(XX.XX - XXX.X)							
	Follow-up	XX	XX	XX.XX	XX.XX	[XX.XX,XXX.X]	XX.XX	(XX.XX - XXX.X)	XX	XX	XX.XX	XX.XX	[XX.XX,XXX.X]	XX.XX	(XX.XX - XXX.X)

p-value=X.XXXX

e-CIG VS. IQOS  
Statistical Analysis Plan  
Version 2.0

Doc code:  
BIOSTAT.SAP.02

Pag. 59 of 115

Sponsor: Center for Tobacco Research, Cessation and Prevention, [name]  
Protocol: Progetto e-cig vs IQOS

Table E.6 Summary of EQ-5D Questionnaire (scores). < Group HnB / Group EC >  
Population: <Per-Protocol/Intention-To-Treat/Continuous Quitters>

Parameter	Visit	Observed Values at Visit							Changes From Visit 1 to Visits n						
		N	N miss	Mean	STD	CI 95%	Median	min-max	N	N miss	Mean	STD	CI 95%	Median	min-max
Mobility (1-5)	Visit 1	XX	XX	XX.X	XX.X	[X.X , X.X]	XX.X	(X - X)							
	Visit 4	XX	XX	XX.X	XX.X	[X.X , X.X]	XX.X	(X - X)							
	Visit 5	XX	XX	XX.X	XX.X	[X.X , X.X]	XX.X	(X - X)							
	Visit 6	XX	XX	XX.X	XX.X	[X.X , X.X]	XX.X	(X - X)							
	Visit 7	XX	XX	XX.X	XX.X	[X.X , X.X]	XX.X	(X - X)	XX	XX	XX.X	XX.X	[X.X , X.X]	XX.X	(X - X)

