SpO2	Visit 1	XX	XX	XX.XX	XX.XX	[XX.XX,XXX.X]	XX.XX	(XX.XX - XXX.X)							
	Visit 4	XX	XX	XX.XX	XX.XX	[XX.XX,XXX.X]	XX.XX	(XX.XX - XXX.X)							
	Visit 6	XX	XX	XX.XX	XX.XX	[XX.XX,XXX.X]	XX.XX	(XX.XX - XXX.X)							
	Visit 7	XX	XX	XX.XX	XX.XX	[XX.XX,XXX.X]	XX.XX	(XX.XX - XXX.X)	XX	XX	XX.XX	XX.XX	[XX.XX,XXX.X]	XX.XX	(XX.XX - XXX.X)
...															
Recovery HR	Visit 1	XX	XX	XX.XX	XX.XX	[XX.XX,XXX.X]	XX.XX	(XX.XX - XXX.X)							
	Visit 4	XX	XX	XX.XX	XX.XX	[XX.XX,XXX.X]	XX.XX	(XX.XX - XXX.X)							
	Visit 6	XX	XX	XX.XX	XX.XX	[XX.XX,XXX.X]	XX.XX	(XX.XX - XXX.X)							
	Visit 7	XX	XX	XX.XX	XX.XX	[XX.XX,XXX.X]	XX.XX	(XX.XX - XXX.X)	XX	XX	XX.XX	XX.XX	[XX.XX,XXX.X]	XX.XX	(XX.XX - XXX.X)
SpO2	Visit 1	XX	XX	XX.XX	XX.XX	[XX.XX,XXX.X]	XX.XX	(XX.XX - XXX.X)							
	Visit 4	XX	XX	XX.XX	XX.XX	[XX.XX,XXX.X]	XX.XX	(XX.XX - XXX.X)							
	Visit 6	XX	XX	XX.XX	XX.XX	[XX.XX,XXX.X]	XX.XX	(XX.XX - XXX.X)							
	Visit 7	XX	XX	XX.XX	XX.XX	[XX.XX,XXX.X]	XX.XX	(XX.XX - XXX.X)	XX	XX	XX.XX	XX.XX	[XX.XX,XXX.X]	XX.XX	(XX.XX - XXX.X)

<File: [..]\Work\_In\_Progress\[..]\Statistica\Programmi\xxxxx.sas>  
 <Source: [..]\Work\_In\_Progress\[..]\Gestione Dati\Dati SAS\xxxxx.satd7sas> Generated on XXXXXXXX XX:XX  
 The percentages are calculated on the total of the enrolled patients by group  
 For further information see Listing X.X

Sponsor: Center for Tobacco Research, Cessation and Prevention, [name]  
Protocol: Progetto e-cig vs IQOS

Table E.7b Summary of Step Test - inferential analysis of VO2MAX  
Population: <Per-Protocol/Intention-To-Treat>

		Group HnB	Group EC
VO2MAX	N	XX	XX
	N missing	XX	XX
	Mean	XX.X	XX.X
	Std. deviation	XX.X	XX.X
	Median	XX.X	XX.X
	Q1-Q3	X.X - XX.X	X.X - XX.X
p-value=X.XXXX			

---

<File: [..]\Work\_In\_Progress\[..]\Statistica\Programmi\xxxxx.sas>  
<Source: [..]\Work\_In\_Progress\[..]\Gestione Dati\Dati SAS\xxxxx.satd7sas> Generated on XXXXXXXX XX:XX  
The p-values was derived from the t-test  
For further information see Listing X

	e-CIG VS. IQOS Statistical Analysis Plan Version 2.0	Doc code: BIOSTAT.SAP.02
		Pag. 62 of 115

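### Any HnB-versus-EC p-value for step test or EQ-5D within Continuous Quitters compares groups selected after randomisation; the SAP text appears to plan such tests, and the table shells do not settle it

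*SAP*

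**What the plan says.** SAP section 7 runs the primary and secondary endpoints on the Intention-To-Treat (ITT) and Per-Protocol (PP) populations. For step test and EQ-5D it adds "a further analysis in the subpopulation of the" Continuous Quitters. Section 7.1 says that a Continuous Quitter "is defined as a subject who has a number of conventional cigarette/day equal to zero from Visit 4 to Visit 6". The same section states the primary aim: "The primary endpoint aims to compare the efficacy of HnB and EC in terms of quit rates at week 12".

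Two sections carry the tests.

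- **Section 7.4 (EQ-5D):** "The t-test will be carried out on the differences at final visit to baseline", with a non-parametric alternative. Results are sent to Table E.4a2.
- **Section 7.5 (step test):** "An inferential analysis will be carried out on the changes from baseline by item". Results are sent to Table E.7b.

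Both sections end with the same sentence, "The analysis will be presented by all subjects and" Continuous Quitters. Neither describes an adjustment, gives a caveat about selection after randomisation, or labels the quitter results exploratory.

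**The concern.** Randomisation at Visit 1 makes the two arms comparable as whole groups. It does not make those who stop smoking on HnB comparable with those who stop on EC. Stopping is what the products are meant to influence, so each product may convert a different kind of smoker. A t-test between the two quitter groups then mixes any product effect with differences in who was selected. With few quitters, a non-significant result says little either.

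Step test and EQ-5D are listed in both documents as measures for comparing tobacco harm reduction between the products, and the protocol plans a publication on that comparison. A quitter-only p-value could be read there as a product effect when it reflects selection, or as evidence of no difference when it reflects low power.

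**Working it through.** **1. When membership is fixed.** Randomisation is at baseline, Visit 1 (protocol, Study Design). Membership depends on cigarettes reported from Visit 4 (week 4) to Visit 6 (week 12). The subset is therefore defined wholly after randomisation, by a version of the outcome that section 7.1 compares between arms.

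**2. Whether a between-arm test in quitters is planned.** Text and shells side by side:

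| Item | Population line | p-value? | Arms |
|---|---|---|---|
| SAP 7.4 text (EQ-5D) | all subjects and Continuous Quitters | test described | not stated |
| Shell E.6 (EQ-5D) | "Population: <Per-Protocol/Intention-To-Treat/Continuous Quitters>" | no | one table per arm |
| Shell E.4a2 (cited by 7.4; it is the mCEQ shell) | PP, ITT | yes | HnB and EC columns |
| SAP 7.5 text (step test) | all subjects and Continuous Quitters | inference described | not stated |
| Shell E.7a (step test) | PP, ITT | no | one table per arm |
| Shell E.7b (step test, VO2MAX) | PP, ITT | yes; footnote: "The p-values was derived from the t-test" | HnB and EC columns |
| Shell S.3 (vital signs, SAP 8.3) | Safety, Continuous Quitters | no | one table per arm |

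Where the shells show a test, it is HnB versus EC. The text extends the analyses to quitters, but no shell with a p-value names quitters.

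**3. The plan's own sample size.** Inputs from the protocol's sample size section: reference rate 0.25, margin 0.15, one-sided alpha 0.05, power 0.80; a true difference of 0 is assumed. The Farrington-Manning restricted rates under the null are 0.189 (test) and 0.339 (reference).

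- Null SD: √(0.189×0.811 + 0.339×0.661) = 0.614
- Alternative SD: √(2×0.25×0.75) = 0.612
- n = [(1.645×0.614 + 0.842×0.612)/0.15]² = 103.48 with unrounded inputs, rounded up to 104

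This reproduces the stated 104 per group. The documents give no sample size for the quitter analyses.

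**4. Precision among quitters.** Inputs: 110 per arm and an expected quit rate of 20-25% (SAP section 3). The detectable difference in SD units at two-sided 0.05 and 80% power is (1.96 + 0.84) × √(2/n).

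- 20%: n = 0.20×110 = 22, giving 2.80×√(2/22) = 0.84 SD
- 25%: n = 0.25×110 = 27.5, giving 2.80×√(2/27.5) = 0.76 SD
- All randomised: n = 110, giving 2.80×√(2/110) = 0.38 SD

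The counts apply the planning quit rate to the Visit 4 to Visit 6 definition, which spans a longer period than abstinence since the previous visit; the actual counts may differ.

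**5. Possible selection bias (illustration only).** The assumptions are mine: no product effect, 110 per arm, and a latent trait that drives quitting through a logistic slope and is correlated with the analysed outcome. That outcome must be read as the change score. Rejection is at nominal two-sided 5%.

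| Quit rates | Selection (slope by arm) | Correlation | Quitter difference | Rejection |
|---|---|---|---|---|
| 25%, 25% | same (1, 1) | 0.5 | 0.00 SD | 5% |
| 25%, 10% | same (1, 1) | 0.5 | about 0.09 SD | 5.7% |
| 25%, 25% | one arm only (1, 0) | 0.3 | 0.19 SD | 11% |
| 25%, 25% | one arm only (1, 0) | 0.5 | 0.31 SD | 22% |
| 25%, 25% | opposite (1, −1) | 0.5 | 0.64 SD | 67% |

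The difference across all randomised subjects stays at zero, to simulation error, in every row. Equal quit rates alone do not protect the comparison; what matters is whether the same kinds of smoker quit in each arm.

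**The case against.** The strongest reply is that a between-arm test in quitters is inferred and nowhere stated outright. Section 7 promises only a further analysis, section 5 calls the analysis descriptive in nature, and the outcome shells that name Continuous Quitters (E.6 and S.3) are laid out per arm without a p-value. On that reading the SAP already does most of what is asked, and product comparisons already rest on ITT and PP. This stands in part: text and shells conflict, and the shells favour the harmless reading. It does not dispose of the point, because 7.4 and 7.5 each describe a test and then say the analysis covers quitters. A programmer following the text would produce the p-values.

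A second reply is that no bias has been shown. That is correct. The outcome is a change from baseline, so a stable difference in fitness between the quitter groups would cancel. Bias arises only if the change itself is related to who quits, and differently by arm. The documents give no evidence on that, and if selection and quit rates are the same in both arms the bias is zero.

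A reader might also infer more than the documents support:

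- **Vital signs.** SAP section 8 plans vital signs in quitters too, but section 8.3 and shell S.3 are descriptive. There is no test to remove.
- **The non-inferiority conclusion.** It is not affected. The quitter output is supplementary to secondary endpoints.
- **No eCO condition in the Continuous Quitter definition.** This is a question about the definition of quitting and is separate from conditioning on it.

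**Conclusion.** The point holds as a minor one. The principle needs no figure: Continuous Quitter status arises after randomisation and may be affected by the product, so a between-arm p-value in that subset is not a randomised comparison. The SAP text appears to call for such p-values and plans no adjustment or caveat, while the shells leave the matter unresolved. The size of any bias cannot be established from the documents; the simulated range of 0 to 0.64 SD shows only how far it depends on assumed selection. The imprecision is firmer: about 22-27 quitters per arm and a detectable difference of about 0.76-0.84 SD, provided the planned 20-25% quit rate also applies to the Visit 4 to Visit 6 definition.

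**What to change.** - In SAP 7.4 and 7.5, state that Continuous Quitter output is exploratory and limited to within-arm changes from baseline with 95% intervals, with no between-arm p-value.
- Keep the HnB-versus-EC comparisons of step test and EQ-5D on the ITT population.
- If a between-arm contrast among quitters is shown at all, adjust it for the baseline value and label it non-randomised. Baseline adjustment does not make it a randomised comparison.
- Align the shells with the text: E.6, E.7a and E.7b on population and p-value, and the reference in 7.4 to E.4a2, which is the mCEQ table.
- In section 8.3, add only the same exploratory label.

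The cost is a few supplementary p-values and some editing of shells. The downside is that there is no formal product test among quitters; the descriptive information on them is kept.

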## 7.1 Analysis of primary endpoint

The primary endpoint aims to compare the efficacy of HnB and EC in terms of quit rates at week 12 by means a non-inferiority threshold of 15%.

A "Continuous Quitter" is defined as a subject who has a number of conventional cigarette/day equal to zero from Visit 4 to Visit 6. The Farrington-Manning Score Test for Proportion Difference will be used for comparing the quit rates of the two groups. The SAS® PROC FREQ with the METHOD=FM option will be used. The quit rates of the two groups, along with the relevant 95% Confidence Intervals, will be summarized in Table E.1 (Appendix 2).

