### **Objectives:**

#### *Primary endpoint:*

1) to compare the **efficacy** of HnB and EC, in terms of quit rates at week 12, by self-reporting abstinence from classic cigarette [validated by an Exhaled breath Carbon monoxide (eCO) measurement  $\leq 10\text{ppm}$ ]

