### **Efficacy assessment:**

The **efficacy** of HnB and EC, in terms of quit rates, will be assessed by self-reporting abstinence from classic cigarette [validated by an Exhaled breath Carbon monoxide (eCO) measurement  $\leq 10$ ppm]. Abstinence from smoking, defined as complete self-reported abstinence from tobacco smoking - not even a puff (together with an eCO concentration of  $\leq 10$ ppm) since the previous study visit, will be calculated at each study visit (“quitters”), including at week 24. Primary endpoint is, however, fixed at week 12.

1. Caponnetto P, Campagna D, Cibella F, et al. (2013a) Efficiency and Safety of an eElectronic cigarette (ECLAT) as Tobacco Cigarettes Substitute: A Prospective 12-Month Randomized Control Design Study. PLoS One, 8(6):e66317.

---

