### 2.2 Study Objectives

The primary objective of this study is to compare the efficacy of HnB and EC, in terms of quit rates at week 12, by self-reporting abstinence from classic cigarette [validated by an Exhaled breath Carbon monoxide (eCO) measurement  $\leq 10$ ppm].

The secondary objectives are:

- 1) to compare the smoking reduction derived from the use of HnB and EC, intended as a 50% reduction in the number of conventional cigarette/day at week 12, defined through self-reporting;
- 2) to compare the adoption rate, and adherence to product use [by collecting (empty) refill bottles and used heatsticks on a daily basis, verified by a study diary filled daily by the subject];
- 3) to compare the acceptability of HnB and of EC, through the assessment of product satisfaction, risk perception, effects on craving and nicotine withdrawal, product preferences, subjective and sensorial effects by:
  - a) Modified Cigarette Evaluation Questionnaire (mCEQ) adapted for EC and HnB users;
  - b) three of 8 items of "Smoking Cue Appeal" adapted for EC and HnBusers;
  - c) "Intent to use questionnaire" (ITUQ) – items 4-6;
  - d) PRI-P CC Perceived Health Risk scale (for classic cigarette)
  - e) PRI-P RRP Perceived Health Risk scale (for reduced risk products)
  - f) percentage of choice of a particular subtype of heatstick (HnB) or e-liquid.
- 4) to compare the tolerability of HnB and EC, in terms of: self-reported adverse and serious adverse events by study participants, vital signs (BP, HR and body weight) measurements.
- 5) to compare the tobacco harm reduction between HnB and EC, in terms of:
  - a) changes in Biomarkers of Biological Effects (BoBE) such as: eCO in the exhaled breath (i.e. eCO), step test values;

	
e-CIG VS. IQOS Statistical Analysis Plan Version 2.0
	Doc code: BIOSTAT.SAP.02
		Pag. 8 of 115

b) measurement of 14 selected Biomarkers of Exposure (BoE) in spot urine samples of study participants:

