## 5 GENERAL INFORMATION FOR THE ANALYSES

	
e-CIG VS. IQOS Statistical Analysis Plan Version 2.0
	Doc code: BIOSTAT.SAP.02
		Pag. 10 of 115

According to the study protocol the statistical analysis will be descriptive in nature.

All the data will be described using standard descriptive statistics, i.e. n, missing, mean, standard deviation, (25th, 50th, 75th) percentiles for numerical variables. As for the categorical variables, frequency tables with count and percentage will be used. In the core of the Statistical Report, the continuous variables will be presented as mean values  $\pm$  standard deviation (SD) or median value and interquartile range [IQR], and categorical variables as numbers and percentages. The descriptive analyses will be presented by group. As indicated in the study protocol, for the primary endpoint, the quit rate at 3 months in the experimental study group will be calculated with a non-inferiority threshold of 15%. The quit rates will be evaluated on an intention-to-treat basis: subjects known to have failed will be considered as treatment failures in the primary analysis along with subjects lost to follow-up.

All the analyses will be performed using SAS® Vers. 9.4.

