## EFFICACY ENDPOINTS

	e-CIG VS. IQOS Statistical Analysis Plan Version 2.0	Doc code: BIOSTAT.SAP.02
		Pag. 42 of 115

Sponsor: Center for Tobacco Research, Cessation and Prevention, [name]  
Protocol: Progetto e-cig vs IQOS

Table E.1a Summary of the Primary End-point. Quit Rate at all visits  
Population: <Per-Protocol/Intention-To-Treat>

			Group HnB N=XXXX	Group EC N=XXXX
Quit rate	Visit 1	N(%)	XXX (XX.X%)	XXX (XX.X%)
	Visit 2	N(%)	XXX (XX.X%)	XXX (XX.X%)
	...	N(%)	XXX (XX.X%)	XXX (XX.X%)
	Visit n	N(%)	XXX (XX.X%)	XXX (XX.X%)

<File: [..]\Work\_In\_Progress\[..]\Statistica\Programmi\xxxxx.sas>

<Source: [..]\Work\_In\_Progress\[..]\Gestione Dati\Dati SAS\xxxxx.sas7bdat>      Generated on XXXXXXXXXX XX:XX

As for the PP population, a "Continuous Quitter" is defined as the subject who did not smoke conventional cigarettes from visit 4 to visit 6

The p-value was derived from the XXXX test

For further information see Listing X.X

Sponsor: Center for Tobacco Research, Cessation and Prevention, [name]  
Protocol: Progetto e-cig vs IQOS

Table E.1b Summary of the Primary End-point. Quit Rate at final visit comparison  
Population: <Per-Protocol/Intention-To-Treat>

		Group HnB N=XXXX	Group EC N=XXXX
Quit Rate	Rate 95%CI	XX.X% [XX.XX,XXX.X]	XX.X% [XX.XX,XXX.X]

H0: P1-P2 ≤ -Margin  
H1: P1-P2 > -Margin

Margin=X.XXX

Score (Farrington-Manning)

Proportion Difference	ASE (F-M)	Z	Pr>Z
X.XXXX	X.XXXX	X.XXXX	X.XXXX

Noninferiority Limit	95% Confedent Limits	
X.XXXX	X.XXXX	X.XXXX

<File: [..]\Work\_In\_Progress\[..]\Statistica\Programmi\xxxxx.sas>

<Source: [..]\Work\_In\_Progress\[..]\Gestione Dati\Dati SAS\xxxxx.sas7bdat>      Generated on XXXXXXXXXX XX:XX

As for the PP population, a "Continuous Quitter" is defined as the subject who did not smoke conventional cigarettes from visit 4 to visit 6  
For further information see Listing X.X

	e-CIG VS. IQOS Statistical Analysis Plan Version 2.0	Doc code: BIOSTAT.SAP.02
		Pag. 44 of 115

Sponsor: Center for Tobacco Research, Cessation and Prevention, [name]  
Protocol: Progetto e-cig vs IQOS

Table E.2a Summary of Smoking Reduction derived from the use of HnB and EC at week 12  
Population: <Per-Protocol/Intention-To-Treat>

		Group HnB	Group EC	p-value
		N=XXXX	N=XXXX	
Smoking Reduction	Rate 95%CI	XX.X% [XX.XX,XXX.X]	XX.X% [XX.XX,XXX.X]	X.XXXX

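### SAP 7.1 does not name the protocol's eCO-verified week-12 quitter as the tested variable; its only quitter definition is unverified self-report over Visits 4 to 6

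*SAP*

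**What the plan says.** **Protocol.** The primary endpoint (Objectives) is the week-12 quit rate, measured "by self-reporting abstinence from classic cigarette [validated by an Exhaled breath Carbon monoxide (eCO) measurement" of at most 10 ppm. The Efficacy assessment section makes this operational. Abstinence is "defined as complete self-reported abstinence from tobacco smoking - not even a puff (together with an eCO concentration of" at most 10 ppm), counted since the previous study visit, with the primary time point fixed at week 12. At Visit 6 the window therefore runs from Visit 5.

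**SAP 2.2** restates the objective with eCO: "in terms of quit rates at week 12, by self-reporting abstinence from classic cigarette [validated by an Exhaled breath Carbon monoxide (eCO) measurement" of at most 10 ppm.

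**SAP 7.1** gives the endpoint as week-12 quit rates with a 15% threshold and does not mention eCO. It says a Continuous Quitter "is defined as a subject who has a number of conventional cigarette/day equal to zero from Visit 4 to Visit 6". The next sentence names the Farrington-Manning test for comparing the quit rates.

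**SAP 7** also uses the term as a subgroup label: "as for the Step Test and the Quality of Life (i.e. EQ-5D), a further analysis in the subpopulation of the" Continuous Quitter. Sections 7.4, 7.5 and 8 use it the same way.

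**SAP Appendix 2.** Tables E.1a and E.1b carry one quitter definition, in a footnote that refers to the PP population: a Continuous Quitter "is defined as the subject who did not smoke conventional cigarettes from visit 4 to visit 6". Both tables are to be produced for PP and ITT. E.1a reports every visit from Visit 1. E.1b is headed "Table E.1b Summary of the Primary End-point. Quit Rate at final visit comparison". An eCO-checked 12-week rate is planned only in Table E.2b, the Russell Standard table under smoking reduction.

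**Drop-outs.** SAP 5 says that "subjects known to have failed will be considered as treatment failures in the primary analysis along with subjects lost to follow-up".

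**The concern.** The section that specifies the primary test and the two tables that report it do not carry the protocol's outcome. Two programmers working from the SAP could test different variables and both claim to have followed it. The footnote wording also leaves it open whether ITT and PP share one outcome.

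The Continuous Quitter rule departs from the protocol in two opposite ways. It is stricter on duration (weeks 4 to 12 instead of weeks 8 to 12) and looser on verification (no eCO). It can therefore raise or lower the chance of a non-inferiority claim. The trial is open label, so unverified self-report may differ between arms, and a difference between arms is what the test measures.

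The version history shows that the definition entered 7.1 in version 1.1 of 4 June 2020, six days before the data review meeting. Nothing in the documents shows that results had been seen. Leaving more than one admissible primary variable at that stage still allows the choice to be made after the data are known.

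**Working it through.** **1. The definitions side by side**

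| Feature | Protocol; SAP 2.2 for eCO | SAP 7.1 and footnotes of E.1a/E.1b |
|---|---|---|
| Window at week 12 | since Visit 5 (about 4 weeks) | Visit 4 to Visit 6 (about 8 weeks) |
| Verification | eCO at most 10 ppm | none |
| Population | all subjects | not limited in 7.1; footnote refers to PP |
| Usable at each visit | yes | no |

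If the Continuous Quitter is the tested variable, it conflicts with the protocol and with SAP 2.2. If it is only a subgroup label, 7.1 and its tables have no operational definition of the primary variable. Either way the section needs correcting.

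**2. The plan's own figure**

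Inputs from the protocol's sample size section: both rates 0.25, margin 0.15, one-sided alpha 0.05, power 0.80. The Farrington-Manning restricted null rates are 0.189 and 0.339.

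n = [(1.645 × √(0.189×0.811 + 0.339×0.661) + 0.842 × √(2×0.25×0.75)) / 0.15]² = 103.5, rounded up to 104 per arm. This matches the plan. The definition of the outcome does not change this number.

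**3. What a different variable does to the planned test**

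I computed z = (p_HnB − p_EC + 0.15) / SE for all 111 × 111 outcomes with 110 per arm, where SE uses the restricted null rates. I summed the binomial probabilities of outcomes with z > 1.645. The documents give no misreport or retention rates, so those below are assumptions.

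With a fraction f of non-quitters wrongly reporting abstinence, the observed rate is p + (1 − p)f. For example, with f = 0.05 in HnB: 0.10 + 0.90×0.05 = 0.145.

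| Assumed false claims (f) | Declared non-inferior, true 10% vs 25% | Power, true 25% vs 25% |
|---|---|---|
| none | 5.0% | 82.5% |
| 5% in both arms | 6.6% | 79.7% |
| 10% in both arms | 8.4% | 77.5% |
| 20% in both arms | 12.4% | 73.4% |
| 5% in HnB only | 21.1% | 93.4% |
| 5% in EC only | 0.9% | 59.8% |

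With the longer window keeping a share r of protocol quitters, the observed rate is r × p.

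| Assumed retention (r) | Observed difference from 10% vs 25% | Declared non-inferior | Power, true 25% vs 25% |
|---|---|---|---|
| 90% in both arms | −13.5 points | 8.9% | 84.8% |
| 80% in both arms | −12.0 points | 15.5% | 87.1% |
| 70% in both arms | −10.5 points | 25.7% | 89.6% |
| HnB 60%, EC 90% | −16.5 points | 2.4% | not computed |
| HnB 90%, EC 60% | −6.0 points | 63.8% | not computed |

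Both effects together (80% retained and 5% false claims among the original non-quitters, both arms) give 17.8%. If relapsed quitters misreport as well, the figure is 17.0%.

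**4. The decision boundary**

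With 27 of 110 quitters on EC, the test passes at 21 of 110 on HnB (z = 1.711) and fails at 20 (z = 1.561).

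**The case against.** The best defence is that the right definition is already in both documents. SAP 2.2 restates the eCO criterion, SAP 1 bases the plan on the protocol, and SAP 5 introduces the primary analysis by reference to the protocol. The SAP never says that the Farrington-Manning test uses the Continuous Quitter. The term serves as a subgroup label elsewhere, the E.1b title points to a single visit, and E.1a cannot be filled with a Visit 4 to Visit 6 rule. On this reading 7.1 has a drafting ambiguity and no changed endpoint. Table E.2b and the by-subject listing of cigarettes and eCO (D.4b) would expose any divergence.

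Most of this is right as description. Substitution is not proven, and the absence of an eCO-based definition is confined to 7.1 and its two tables. But an objective in section 2 does not tell the programmer which variable enters the test when the analysis section gives a different rule directly before naming that test. E.2b does not carry the non-inferiority test.

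The numbers also need care:

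- The retention results are errors only against the protocol outcome. In all but the HnB 60%, EC 90% case, the difference on the longer-window outcome lies inside the margin.
- The rise under equal retention comes from applying a fixed absolute margin to lower rates and has nothing to do with eCO.
- The 60% and 90% split is arbitrary.
- Under the Visit 4 to Visit 6 rule a false quitter must report zero throughout that period, which may make high misreport rates less plausible.
- Any binary test has a boundary where one subject decides, so step 4 shows sensitivity and does not show bias.

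These points limit how far the figures can be pressed. They do not remove the contradiction.

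**Conclusion.** The concern holds and should be corrected before the primary analysis is run. SAP 7.1 and Tables E.1a and E.1b do not specify the eCO-verified week-12 quitter that the protocol and SAP 2.2 require. As written, they allow the sole primary test to run on a longer, unverified outcome.

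That the definitions differ is certain from the text. The size and direction of the effect are not. Equal misreporting of 5% to 10% moves the 5.0% error rate modestly, to 6.6% to 8.4%. Misreporting of 5% in one arm only moves it to 21.1% or 0.9%, and moves power from 82.5% to 93.4% or 59.8%. These results assume 110 per arm, a 15% margin, a one-sided 5% test and the stated misreport rates, none of which can be checked against the documents. The required 104 per arm is unaffected.

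**What to change.** 1. In SAP 7.1 and Tables E.1a and E.1b, for both ITT and PP, state that the variable tested by Farrington-Manning is: no conventional cigarette, not even a puff, by self-report since Visit 5, **and** eCO of at most 10 ppm at Visit 6.
2. Drop-outs already count as failures (SAP 5 and section 2.4 of the data review minutes). Add that a subject who attends Visit 6 with a missing report or missing eCO also counts as not quit. The protocol's two-part definition implies this, but it should be written down.
3. In E.1a apply the same rule at each other post-baseline visit, counting from the previous visit. In E.1b state that the final visit means Visit 6, since Visit 7 is the follow-up.
4. Remove the PP-specific footnote from both primary tables. Keep Continuous Quitter as a secondary outcome and subgroup label.
5. As a minor point, align the eCO cut-off in the E.2b footnote (below 10 ppm) with the protocol (at most 10 ppm).

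The cost is SAP wording and table footnotes. No new data are needed, because eCO is scheduled at every visit from Visit 1 to Visit 7. The verified quit rate may be lower than the self-reported one, by an amount the documents do not allow one to estimate.
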